12.5.2.1. Handling of Missing and Partial Dates

Element	Reporting Detail
General	
 Partial dates will be displayed as captured in participant listing displays.
Adverse Events	
 The eCRF allows for the possibility of partial dates (i.e., only month and year) to be recorded for AE start and end dates; that is, the day of the month may be missing. In such a case, the following conventions will be applied for calculating the time to onset and the duration of the event: 
 Missing Start Day: First of the month will be used unless this is before the start date of study treatment; in this case the study treatment start date will be used and hence the event is considered On-treatment as per Appendix 2 Missing Start Time: Midnight 0:00:00 will be used for AEs with missing start time to determine if it's AChE-I.

Element	Reporting Detail
	
 ○ Missing Stop Day: Last day of the month will be used, unless this is after the stop date of study treatment; in this case date the study treatment stop date will be used. ● Completely missing start or end dates will remain missing, with no imputation applied. Consequently, time to onset and duration of such events will be missing. ● Adverse events with entirely missing or unknown start dates will be assumed to be on-treatment and also treatment emergent for reporting purposes.
Concomitant Medications/ Medical History	
 ● Partial dates for any concomitant medications recorded in the CRF will be imputed using the following convention: 
 ○ If the partial date is a start date, a '01' will be used for the day and 'Jan' will be used for the month ○ If the partial date is a stop date, a '28/29/30/31' will be used for the day (dependent on the month and year) and 'Dec' will be used for the month ● The recorded partial date will be displayed in listings.

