8.2.3. Acetylcholinesterase-Inhibition Adverse Events

Any reported AE listed in the table in Section 12.4.3 with a start time no later than 12 hours after the last dose administered, as evaluated by the investigator as per the DMID grading criteria provided in in protocol Section 12.5 and Appendix 7, will be included in the programmatic identification of AChE-I related AESI. The list of preferred terms for

programming to be considered due to potential AChE-I is provided in Appendix 4 (Section 12.4.3).

Cumulative grade score of Acetylcholinesterase-Inhibition (AChE-I) will be calculated as the sum of the grade of each reported AE. This enables the number of AEs and the severity of each AE to be considered. The grading scale is defined as

Cumulative Grade:	0	1	2	3	4
Cumulative Grade Score:	0	1 to 3	4 to 6	7 to 10	>=11

For instance, if a participant reports two AEs, one of Grade 1 and the other of Grade 3 their cumulative grade score of 4 would result in cumulative grade 2. This will be calculated for All AChE-I events, non-GI AChE-I events and GI AChE-I events.

Acetylcholinesterase inhibition AESIs will be listed and tabulated by SOC and preferred term and maximum grade. Non-GI AChE-I events will also be summarized. A separate table will summarize the AChE-I AESI by the number of events and unique preferred terms. In addition, time of onset (time from first dose to the onset of first event in hours), duration, and lag time (the time from last dose to the end date/time of the last event for subjects whose end date/time of the last event is after treatment end date/time) of AChE-I event will also be summarized and repeated for non-GI AChE-I and GI AChE-I events. AChE-I events with a start time less than 6 hours after the latest dose administered will also be flagged in listings.

Graphical presentation via stacked bar charts of percentage of subjects in each AChE-I cumulative grade will be produced for All AChE-I events and non-GI AChE-I events separately. In addition, a forest plot of relative risk of AChE-I events between two treatment groups and its 95% Wald CI for each event will also be included. The details of the planned displays are provided in Appendix 9.

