12.2. Appendix 2: Study Phases and Treatment Emergent Adverse Events

12.2.1. Study Phases

Assessments and events will be classified according to the time of occurrence relative to the start and end date of study treatment.

Study Phase	Definition
Pre-Treatment	Date/Time < Study Treatment Start Date/Time
On-Treatment	Study Treatment Start Date and Time < Date and Time ≤ Study Treatment Stop Date and Time
Post-Treatment	Date and Time > Study Treatment Stop Date and Time

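### The missing AE start time rule has no floor at first dose, so hour-based onset of untimed first-dose-day AChE-I events is either negative or undefined

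*SAP*

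**What the plan says.** SAP Section 12.5.2.1 covers missing and partial AE dates. Its lead-in, written about records where the day of the month is missing, says "the following conventions will be applied for calculating the time to onset and the duration of the event". Two of the bullets beneath it matter here:

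- Missing start day: "First of the month will be used unless this is before the start date of study treatment", in which case the treatment start date replaces it.
- Missing start time: "Midnight 0:00:00 will be used for AEs with missing start time"; the sentence goes on to give the purpose as deciding whether the event is AChE-I. No lower limit is given.

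SAP Section 8.2.3 defines an AChE-I event of special interest as a listed term "with a start time no later than 12 hours after the last dose administered". It sets no lower limit. It then summarizes onset in hours from the first dose to the participant's first such event, together with duration and lag. These go to Tables 3.121 and 3.122; the programming note for Table 3.121 asks for mean, median, maximum and minimum. The same section plans "a forest plot of relative risk of AChE-I events between two treatment groups".

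The footnotes to SAP Table 5 start AE recording at the first dose, and Protocol Section 9.2.1 sends occurrences between consent and treatment to medical history. The treatment-emergent flag in SAP Appendix 2 compares dates only when the time is missing.

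**The concern.** A recorded AE dated on the first-dose day must, by the plan's own collection rule, have begun at or after the first dose. Midnight at the start of that day is therefore a value the event cannot have. The missing-day rule anticipates this problem and has a floor; the missing-time rule does not.

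At stake are the AChE-I onset and duration tables. Onset uses each participant's first event, and an untimed first-dose-day event set to midnight always ranks first, ahead of any timed event that day. If the value is used, a single such record makes the minimum in Table 3.121 negative. If it is not used, the programmer has no instruction. AChE inhibition is listed as a potential risk of gepotidacin in Protocol Section 3.3.1, so these tables will be read closely.

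**Working it through.** The plan states no figure here, so there is none to reproduce. The check is clock arithmetic on the SAP's rules.

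**Inputs.** T is the clock hour of first dose on Day 1, and Day 2 midnight is hour 24. The second gepotidacin dose comes 10 to 12 h after the first (SAP Section 2.3); the comparator is given once, at T. The AChE-I window closes 12 h after the last dose (SAP Section 8.2.3): T+22 to T+24 for gepotidacin with both doses, T+12 for the comparator. The documents do not fix T, so the ranges below are assumptions.

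**First-dose date.** Midnight is hour 0.

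- Onset if midnight is used: 0 - T = -T. For T = 9, 13 and 17 this is -9, -13 and -17 h.
- Onset with a floor at first dose: max(0, T) - T = 0 h.
- Duration: the true start is at or after T, so starting the clock at 0 adds at least T hours.
- AChE-I class: hours 0 and T both precede the window's close in both arms, so the floor changes nothing.

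**Day 2.** Midnight is hour 24.

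- Gepotidacin, both doses: counted if T+22 ≥ 24 at the shortest gap, so always for T ≥ 02:00.
- Comparator: counted if T+12 ≥ 24, so only for T ≥ 12:00.
- A floor at first dose does not act, because hour 24 is already 24 - T hours after dosing (15, 11 and 7 h for T = 9, 13 and 17).

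The next table compares the share of untimed Day 2 events counted with the share truly in the window. It assumes T uniform over the range shown, an 11 h dose gap and Day 2 onset uniform over 24 h. The true share is the mean of (T-1)/24 for gepotidacin and of max(T-12, 0)/24 for the comparator. For 09-17 h: gepotidacin (13-1)/24 = 50.0%; comparator 0.625 × 2.5/24 = 6.5%.

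| First dose (assumed) | Counted: gepotidacin v comparator | Gap (points) | Truly in window | Gap (points) |
|---|---|---|---|---|
| 08-12 h | 100% v 0% | 100 | 37.5% v 0% | 37.5 |
| 08-16 h | 100% v 50% | 50 | 45.8% v 4.2% | 41.7 |
| 09-17 h | 100% v 62.5% | 37.5 | 50.0% v 6.5% | 43.5 |
| 12-17 h | 100% v 100% | 0 | 56.3% v 10.4% | 45.8 |

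The last column shows that the arms differ even when times are known. Midnight imputation widens that gap in the first two rows and narrows it in the last two.

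**The case against.** The strongest reply is that the missing-time bullet limits itself to AChE-I determination, and that its lead-in concerns records with a missing day, not a missing time. On that reading midnight never reaches the onset tables. This stands in part: negative onset is the natural reading of a bullet placed in a list about onset and duration, but not the only one. A reader might infer that Tables 3.121 and 3.122 are certain to contain negative values. The documents do not support that, since it also requires untimed events to occur. What survives is that no other rule says how to derive onset in hours without a time.

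Earliest-time imputation is also a recognizable inclusive convention, in line with the SAP treating missing severity as severe and missing relationship as related. That defends midnight for deciding membership of the AChE-I set. It does not defend a start before dosing in an onset summary.

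A reader might further infer that these events fall into the pre-treatment phase, defined in Appendix 2 as "Date/Time < Study Treatment Start Date/Time". Section 12.5.2.1 does not send the midnight value there, and AE summary tables rest on treatment emergence, which Appendix 2 judges by date when the time is missing. No planned output has been identified that would change.

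**Conclusion.** The point holds as a minor gap in the SAP. For an untimed AChE-I event on the first-dose date, onset is either -T hours, with duration overstated by at least T hours, or has no derivation rule. AChE-I classification there, the treatment-emergent flag and all efficacy analyses are unaffected. Overall impact depends on the share of untimed AEs and, for size, on dosing clock times; the documents give neither.

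The Day 2 effect is secondary and has a different cause. It is tempting to blame the missing floor for it, but a floor changes no Day 2 classification. It comes from anchoring the 12 h window on the last dose, combined with earliest-time imputation. Nor can one infer a bias in a fixed direction: the arm gap moved from 37.5 to 100 points under one assumed dosing range and from 45.8 to 0 under another. Nor does the effect persist whatever the window length: with a 24 h window the comparator window closes at T+24, so Day 2 midnight falls inside it in both arms.

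**What to change.** Replace the missing-time bullet in SAP Section 12.5.2.1 with wording to this effect:

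*If the AE start time is missing and the start date is the first-dose date, impute the first-dose time. For later dates, use midnight only for AChE-I classification, and exclude the event from the hour-based onset, duration and lag summaries.*

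Lag runs from last dose to the end of the last event, so a missing start time does not distort it; excluding it there simply keeps the three summaries on the same events. The treatment-emergent flag should keep its date comparison.

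Report the number of untimed listed-term events by arm. For Day 2, add a sensitivity analysis of the AChE-I incidence and relative risk with all untimed Day 2 events counted, then with none counted.

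The cost is a sentence of SAP text, one derivation, one count and one small sensitivity output. Untimed events after the first-dose date leave the hour-based summaries. The change is best settled before unblinding.

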12.6. Appendix 6: Values of Potential Clinical Importance

12.6.1. ECG

ECG Parameter	Units	Potential Clinically Important Range	
		Lower	Upper
Absolute			
Absolute QTc Interval	msec		>450
Absolute PR Interval	msec	< 110	> 220
Absolute QRS Interval	msec	< 75	> 110

NOTES:

1. Represent further subdivisions of ECG values for analysis.

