3.3.1. Risk Assessment

Potential Risk of Clinical Significance	Summary of Data/Rationale for Risk	Mitigation Strategy
Gepotidacin (GSK2140944)		

Cardiovascular Effects
 
Based on nonclinical data, cardiovascular effects were reversible increase in heart rate and blood pressure (dog and monkey); reversible 10 to 21 msec (4% to 9%) increase in QTc (monkey); and at the highest dose, a reversible 2 to 3 msec (6% to 8%) increase in QRS (monkey).
 
Based on a thorough QTc clinical study, gepotidacin may cause mild, reversible heart rate effects and QT prolongation.
	
In a thorough QTc study, infusion of gepotidacin at doses of 1000 and 1800 mg over 2 hours caused a mild increased heart rate effect of approximately 6 to 10 bpm and QT prolongation measured as $\Delta\Delta\text{QTcF}$ of 12 to 22 msec. The QT prolongation evolved during the infusion and was quickly reversed over 2 hours after the end of the infusion (see Section 5.2.6 and Section 6 of the IB).
 
In Phase I and II studies, concentration-dependent QT prolongation has been observed during clinical trials with gepotidacin; however, this increase has not translated into medically significant QTc values or changes from baseline ($\text{QTcF} > 500$ msec or change from baseline > 60 msec) or cardiovascular safety concerns.
 
In Phase I and II studies, gepotidacin did not have a clinically relevant effect on cardiac conduction (PR and QRS intervals).
	
See Section 6.2 for excluded cardiac conditions. Close monitoring of clinical parameters and AEs (Section 2, Table 1) will be conducted, and treatment monitoring and evaluation criteria (Section 8.1.2) will be utilized to mitigate cardiovascular effects.
 
Participants taking medications known to increase QT or potent CYP3A4 inhibitors will be excluded (Section 7.7.2).
 
See also the Hepatic and Renal sections within this table below.

Potential Risk of Clinical Significance	Summary of Data/Rationale for Risk	Mitigation Strategy

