8.1.2. QTc Stopping Criteria

- This protocol only requires an ECG evaluation at the Baseline Visit. Should further ECG monitoring or evaluation be needed for an individual participant, per investigator discretion, the following should be considered:
- Further monitoring and/or evaluation should be considered in any participant who meets either of the bulleted criteria below:
 - QTc > 500 msec OR uncorrected QT > 600 msec
 - Change from baseline of QTc > 60 msec

For participants with underlying bundle-branch block, follow the evaluation criteria listed below:

Baseline QTc With Bundle-Branch Block	Criteria for Further Evaluation and Monitoring of QTc With Bundle-Branch Block
< 450 msec	> 500 msec
450 to 480 msec	≥ 530 msec

- The *same* QT correction formula *must* be used for *each individual participant* to determine eligibility for the study and whether further evaluation and/or monitoring are necessary. This formula may not be changed or substituted once the participant has been enrolled. (Note: Ideally, all ECGs for a participant should be performed with the same ECG machine.)
 - For example, if a participant is eligible for the protocol based on QTcB, then QTcB must be used for discontinuation of this individual participant as well.
 - Once the QT correction formula has been chosen for a participant's eligibility, the same formula must continue to be used for that participant for all QTc data being collected for data analysis. Safety ECGs and other nonprotocol-specified ECGs are an exception.
- The QTc should be based on averaged QTc values of triplicate ECGs obtained over a brief (e.g., 5- to 10-minute) recording period.

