8.4. Vital Signs and ECG

The analyses of non-laboratory safety test results including ECGs and vital signs will be based on GSK Core Data Standards, unless otherwise specified. Summary tables will be provided for vital signs change from baseline values, and worst post-baseline vital signs results relative to baseline results. Participants with missing baseline values are assumed to have within range baseline values.

The arithmetic mean of the three recorded ECG measurements will be employed in all data summaries and participant listings. ECG measurements at baseline will be recorded, including heart rate, PR interval, QRS duration, QT interval, QRS axis and RR interval. When not entered directly on eCRF, corrected QT intervals will be calculated by Bazett's formula:

$$QTcB (msec) = \frac{QT}{\sqrt{RR/1000}}$$

and by Fridericia's formula:

$$QTcF (msec) = \frac{QT}{\sqrt[3]{RR/1000}}$$

depending on the availability of other measurements. ECGs may be collected after start of treatment, when medically warranted. In such cases, change from baseline in measurements will be derived.

Listings will be provided for baseline abnormal ECG findings, ECG values of potential clinical importance, and vital sign values of potential clinical importance. Details of the ECG values or vital signs of potential clinical importance are provided in Appendix 6. The details of data displays are presented in Appendix 9.

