Serious and Other Significant Adverse Events					
801	Safety	AE14	Listing of Serious Adverse Events (Fatal and Non-Fatal)	ICH Listing	DS, SAC
802	Safety	AE8CP	Listing of Adverse Events of Special Interest	ICH Listing	DS, SAC
803	Safety	SAFE_L1	Listing of Deaths	ICH Listing	DS, SAC
All Laboratory					
901	Safety	LB5A	Listing of Clinical Chemistry Toxicities of Grade 3 or Higher	ICH Listing	DS, SAC
902	Safety	LB5A	Listing of All Clinical Chemistry Data for Participants with Toxicities of Grade 3 or Higher	ICH Listing	DS, SAC
903	Safety	LB5A	Listing of Hematology Toxicities of Grade 3 or Higher	ICH Listing	DS, SAC

ICH: Listings					
No.	Population	IDSL / Example Shell	Title	ICH/Non-ICH & Programming Notes	Deliverable
904	Safety	LB5A	Listing of Hematology Data for Participants with Toxicities of Grade 3 or Higher	ICH Listing	DS, SAC
905	Safety	LB5A	Listing of Serology Results	ICH Listing	
906	Safety	UR2A	Listing of Urinalysis Data	ICH Listing	DS, SAC
ECG					
1001	Safety	EG5	Listing of All ECG Findings for Participants with an Abnormal Finding	Non-ICH Listing	DS, SAC
1002	Safety	EG3	Listing of All ECG Values for Participants with Any Value of Potential Clinical Importance	Non-ICH Listing	DS, SAC
Vital Signs					
1101	Safety	VS4	Listing of All Vital Signs for Participants with Potential Clinical Importance Values	Non-ICH Listing	DS, SAC
Liver Events and Other Safety Endpoints					
1201	Safety	SAFE_L2	Listing of Clostridium difficile Colitis Results	Non-ICH Listing	DS, SAC
1202	Safety	SU2	Listing of Alcohol Intake at Onset of Liver Event	Non-ICH Listing Conditional Display	DS, SAC
1203	Safety	LIVER5	Listing of Liver Monitoring/Stopping Event Reporting	Non-ICH Listing Conditional Display	DS, SAC
1204	Safety	LIVER7	Listing of Liver Biopsy Details	Non-ICH Listing Conditional Display	DS, SAC
1205	Safety	LIVER8	Listing of Liver Imaging Details	Non-ICH Listing Conditional Display	DS, SAC
1206	Safety	LIVER15	Liver Stopping Event Profile	Non-ICH Listing Conditional Display	DS, SAC

ICH: Listings					
No.	Population	IDSL / Example Shell	Title	ICH/Non-ICH & Programming Notes	Deliverable
1207	Safety	PREG1	Listing of Participants Who Became Pregnant During the Study	Non-ICH Listing Conditional Display	DS, SAC
COVID-19					
1301	Intent-to-Treat	PAN5A	Country Level Listing of Start Dates of Waves of COVID-19 Pandemic Measures	Non-ICH Listing	DS, SAC

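### SAP 12.6.1 has no change-from-baseline QTc row, so a post-dose rise above 60 msec that ends at or below 450 msec does not select a participant for Listing 1002 on QTc

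*SAP*

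**What the plan says.** - **Protocol 8.1.2.** Only the Baseline ECG is required; later ECGs are at the investigator's discretion. For those, the protocol states: "Further monitoring and/or evaluation should be considered in any participant who meets either of the bulleted criteria below". The two criteria are "QTc > 500 msec OR uncorrected QT > 600 msec" and "Change from baseline of QTc > 60 msec". Participants with bundle-branch block have their own absolute limits.
- **Protocol 3.3.1.** On Phase I and II experience with concentration-dependent QT prolongation, it says that "this increase has not translated into medically significant QTc values or changes from baseline", and gives QTcF above 500 msec or a change above 60 msec in parentheses.
- **SAP 8.4.** ECGs may be taken after treatment starts when there is a medical reason. "In such cases, change from baseline in measurements will be derived". No threshold is attached to that change. Both the Bazett and the Fridericia corrections are provided for.
- **SAP 12.6.1.** The limits are "Absolute QTc Interval" above 450 msec, "Absolute PR Interval" below 110 or above 220 msec, and QRS below 75 or above 110 msec. There is no change row, and the correction behind QTc is not named.
- **SAP 12.9.10.** Listing 1002 is titled "Listing of All ECG Values for Participants with Any Value of Potential Clinical Importance". Listing 1001 covers participants with an abnormal ECG finding.

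**The concern.** The protocol gives two routes by which a QTc result deserves a closer look, an absolute value and a change from baseline. The SAP computes the change but selects participants for its clinical-importance listing on absolute values alone. The 450 msec limit is also the general entry ceiling (protocol 6.2, criterion 17), so it marks a high value rather than a movement away from the participant's own baseline.

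At stake is the completeness of one supportive safety listing. Protocol 3.3.1 names QT prolongation as a risk for gepotidacin and for azithromycin, so the question arises in both arms. Since only the Baseline ECG is scheduled, the occasional post-dose ECG is the only QT measurement this trial has on treatment.

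**Working it through.** The plan states no figure on this point, so there is none to reproduce. The check compares the two rules directly.

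**Inputs** (B = baseline QTc, P = post-dose QTc, msec)
- Protocol change criterion (8.1.2): P − B > 60.
- SAP QTc flag (12.6.1): P > 450.
- Entry ceiling (protocol 6.2, criterion 17): B ≤ 450, or ≤ 480 with bundle-branch block. Baselines below 390 are eligible.

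**Step 1: who meets the protocol criterion but not the SAP flag?** Those with B + 60 < P ≤ 450. Such a P exists only if B + 60 < 450, that is, B < 390.

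**Step 2: in whole milliseconds**

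| Baseline QTc | Post-dose QTc with a rise > 60 and no QTc flag |
|---|---|
| 360 | 421 to 450 |
| 370 | 431 to 450 |
| 380 | 441 to 450 |
| 389 | 450 only |
| 390 or more | none |

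For example, 385 to 448 is a rise of 63: above 60, but 448 is not above 450.

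**Step 3: the other direction.** If B ≥ 390, a rise above 60 gives P > 450, so the SAP flag always catches it.

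**Step 4: the absolute criteria.** QTc > 500 is always > 450, so it is already captured. The bundle-branch-block limits (> 500 and ≥ 530) are captured for the same reason. Uncorrected QT > 600 has no row of its own. With the SAP 8.4 formulas, a QT of 600 gives QTc ≤ 450 only if RR ≥ (600/450)² = 1.78 s under Bazett (heart rate 60/1.78, about 34 per minute or slower), or RR ≥ (600/450)³ = 2.37 s under Fridericia (about 25 per minute or slower). In practice the gap is in the change criterion.

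**Step 5: the displays.** The ECG entries in SAP Appendix 9 are Listings 1001 and 1002, on shells EG5 and EG3. There is no ECG table or figure, and neither title mentions change from baseline. Vital signs, by contrast, have a change-from-baseline table (3.301).

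**Step 6: after the change.** If Listing 1002 selects on P > 450 or P − B > 60, the set in Step 1 is empty.

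**The case against.** The strongest reply is that no commitment is broken. The protocol's safety analysis (10.4.3) promises only a listing of baseline ECGs, ECG is not a safety endpoint, and the SAP already goes further. Protocol 8.1.2 is addressed to investigators at the bedside and is not an analysis rule. This stands as a reason for low priority. It does not explain why the SAP derives the change and then does not use it for selection.

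There are also other routes to notice. An out-of-range PR or QRS would bring a participant into Listing 1002, and an abnormal finding might bring one into Listing 1001. Clinically significant ECG changes are reported as adverse events (protocol 9.4.3). QT prolongation goes automatically to the adverse-reaction short list (SAP 8.5.2). These are real but partial: the first two do not respond to the size of a QTc rise, and the last two need an investigator to have judged and reported an event.

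Three stronger readings are tempting, and the documents do not support them.
- A reader might infer that the protocol defines a rise above 60 msec as a QTc signal. Section 8.1.2 makes it a prompt to consider further assessment, and 3.3.1 uses the figure to describe earlier studies.
- A reader might infer that no display shows the change. The EG3 and EG5 shells are not in the documents, so a change column cannot be ruled out. Such a column would not alter who is selected.
- A reader might want a percentage of rises missed. That needs a distribution of baseline QTc, and a count would also need the number of post-dose ECGs. Neither is given, and the count could be zero.

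One caution on interpretation also stands. Protocol 9.4.3 asks for triplicates after baseline only if the first tracing is prolonged, so some changes may set a single reading against a triplicate mean.

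**Conclusion.** The point holds as a reporting mismatch between SAP 12.6.1 and protocol 8.1.2. For any baseline QTc below 390 msec there is a range of post-dose values that meets the protocol's change criterion without triggering the SAP's QTc flag. That result is arithmetic on the two stated limits and needs no distributional assumption. It does assume that Listing 1002 selects on the 12.6.1 limits, as its title and SAP 8.4 indicate, and that PR and QRS are within their limits.

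Its practical size is small. Post-dose ECGs are unscheduled, protocol 3.3.1 reports that earlier studies did not show changes of this size, and the adverse event routes would catch some cases. No efficacy result, endpoint or hypothesis test is affected. The severity is low.

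**What to change.** Reconcile SAP 12.6.1 and Listing 1002 with protocol 8.1.2, for reporting only:
- add the protocol's own change-from-baseline QTc criterion to 12.6.1 as a further selection row;
- let Listing 1002 select on either the absolute or the change row, and show the change already derived under SAP 8.4;
- state which QTc correction the flag uses, and apply the same one to the baseline and post-dose values being compared. Bazett and Fridericia agree only when RR is 1000 msec, and protocol 8.1.2 exempts safety ECGs from its rule of one formula per participant, so pointing to the eligibility formula would not settle this.

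A separate row for QTc above 500 msec is not needed, since the 450 msec limit already selects those participants. The cost is one table row, one listing filter and a sentence on the correction. It needs no new data and leaves participant management as it is.
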